13.3 Primary Objective #1

To characterize the effectiveness of the Integrated Diagnostic Medication Intervention Strategy in resolving subject risk.

13.3.1 Hypothesis

There is no statistical hypothesis for this objective

13.3.2 Endpoint Definition

Once initiated, the Integrated Diagnostic Medication Intervention Strategy will be regarded as being effective if all the following criteria are met:

- The intrathoracic impedance of a subject recovers per defined criterion after completion of the Integrated Diagnostic Medication Intervention;
- The subject has no HF-related event (as adjudicated by the CEC) during or in the next 14 days after completion of the Integrated Diagnostic Medication Intervention;

NOTE: Intervention for heart failure decompensation (HF event) is defined as an event requiring invasive intervention (i.e. IV diuretics, ultrafiltration, or equivalent) or inpatient hospitalization.

- The subject has not experienced any adverse events that are related to the Integrated Diagnostic Medication Intervention per CEC adjudication and require medical care.

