6.4.1 ISCC Executed Acute Medication Intervention (PRN and Counseling)

The ISCC facilitated intervention component will consist of providing reinforcement and direction to the subject as to when they are to self-administer up to two rounds of investigator prescribed PRN to the subject per single transmission that warrants action. The investigator prescribed PRN is initiated after ISCC nurse has ensured that subject has been compliant with their baseline medication regimen including diuretic medications. Each round of PRN will be 3 days long. Thus, no more than 6 days of PRN medication will be administered to the subject.

The example scenario in Figure 6 below is an illustration of this ISCC executed intervention. Referring to Figure 6, the day of the transmission is considered Day 0. Since the OptiVol CareAlert transmission is initiated by the device at 5 PM, the nurse will attempt to contact the patient on the following day (includes weekends). Thus, the ISCC nurse will call the subject via phone on Day 1 (1 day post initial transmission), and upon subject contact, guide the subject to take their first round of investigator prescribed diuretic for 3 days if intervention is warranted (Section 6.3.2 above).

The ISCC nurse will notify the subject's investigator using a 'Interim Patient Report' indicating that the first round of PRN has been initiated (see Appendix B: ISCC Reports to Physician for an example of this report).

One Round of Medication Intervention

[figure not shown]

Figure 6: Example Scenario of One Round of Medication Intervention (PRN).

The efficacy of the PRN is evaluated using raw impedance based recovery criterion. (Refer to section 6.4.1.1 and Figure 8 for a detailed description of determining recover criterion.) Recovery criterion is evaluated on Day 4 (when possible) (4 days post initial transmission or 3 days post PRN initiation) and then again on day 8 (when possible) after first PRN. If the recovery criterion is not met on day 4, a second round of PRN is initiated. The ISCC nurse will notify the subject's investigator using a 'Interim Patient Report' indicating that the second round of PRN has been initiated. Figure 7 illustrates this example scenario of 2 rounds of successive PRNs.

Two Rounds of Medication Intervention

[figure not shown]

Figure 7: Example Scenario of Two Rounds of Medication Intervention (PRN).

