10.5.2 Death classification and reporting

Sufficient information will be required in order to properly classify the subject's death. The Investigator shall classify each subject death per the following definitions:

Cardiac Death: A death directly related to the electrical or mechanical dysfunction of the heart.

Sudden Cardiac Death (SCD): Natural death due to cardiac causes, indicated by abrupt loss of consciousness within one hour of the onset of acute symptoms; preexisting heart disease may have been known to be present, but the time and mode of death are unexpected. If time of onset cannot be determined, SCD will alternatively be defined as any unexpected cardiac death occurring out of the hospital or in the emergency room as dead on arrival.

Non-sudden Cardiac Death: All cardiac deaths that are not classified as sudden deaths, including all cardiac deaths of hospitalized subjects on inotropic support.

Non-cardiac Death: A death not classified as a cardiac death.

Unknown Classification: A death in which there is no clinical evidence to support. Unknown death classification is intended for use only when there is insufficient or inadequate information to classify the death

The CEC will review deaths and provide a final adjudication of the primary cause of death, relatedness, and death classification.

Regulatory reporting of Subject Deaths will be completed according to local regulatory requirements. Refer to Table 16 for a list of required investigator and sponsor reporting requirements and timeframes.

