7.9.2.3. Endpoint Definition

Once initiated, the Integrated Diagnostic Medication Intervention Strategy will be regarded as being safe if all the following criteria are met:

- The Integrated Diagnostic Medication Intervention applied to an episode is not terminated due to safety issues;

NOTE: Safety issues include hypotension with/without patient contact and weight loss with patient contact.

- And, the Integrated Diagnostic Medication Intervention applied to an episode has not caused treatment-related adverse events (as adjudicated by the CEC).

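### An episode with impedance recovery followed by the subject's death at home within 14 days can be scored effective, because no effectiveness criterion counts death

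*Protocol*

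**What the plan says.** Protocol 13.3.2 states that the strategy "will be regarded as being effective if all the following criteria are met". SAP 7.9.1.3 repeats the definition. The criteria are:

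1. "The intrathoracic impedance of a subject recovers per defined criterion after completion of the Integrated Diagnostic Medication Intervention".
2. "The subject has no HF-related event (as adjudicated by the CEC) during or in the next 14 days after completion" of the intervention. A NOTE directly below says that an HF event "is defined as an event requiring invasive intervention (i.e. IV diuretics, ultrafiltration, or equivalent) or inpatient hospitalization".
3. No adverse event that is "related to the Integrated Diagnostic Medication Intervention per CEC adjudication and require medical care".

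On timing, protocol 6.4.1 says: "Recovery criterion is evaluated on Day 4 (when possible"; a further reading follows on Day 8, again when possible.

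The safety endpoint (protocol 13.4.2, SAP 7.9.2.3) has two conditions: the intervention was not terminated for a safety issue, and it "has not caused treatment-related adverse events (as adjudicated by the CEC").

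Deaths are handled elsewhere. Protocol 10.5 requires a death form and an adverse event form, and the CEC adjudicates cause, relatedness and class. The class of sudden cardiac death can include "any unexpected cardiac death occurring out of the hospital or in the emergency room as dead on arrival". Neither document carries the result of this adjudication into the effectiveness endpoint. Neither says how to score a 14-day window cut short by death. Protocol 13.2 and SAP 7.4 both say that the main analysis will not account for missing data.

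**The concern.** Criterion 2 depends on care being delivered: IV-type therapy or an admission. A subject who dies at home receives neither, so the episode passes. Death also rules out any later HF event, so under this criterion it protects the score.

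The endpoint is primary, and its results are to guide the planning of a pivotal study (protocol 5.1 and 13.1). A rule that codes death as success could be carried into that larger study. The sponsor may also stop enrolment or follow-up at an interim analysis on its own judgement that the objectives are sufficiently characterised, and the protocol provides for no data monitoring committee (section 14). The scoring of a death shortly after a study-triggered medication change should be settled before data are seen.

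**Working it through.** **Step 1. Apply the rule to a case.** A subject has one round of PRN, meets the recovery criterion on Day 4, and dies at home on Day 10 with no IV therapy and no admission.

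| Criterion | Result as written |
|---|---|
| 1. Impedance recovery | Met on Day 4 |
| 2. No HF-related event to 14 days after completion | Met under the NOTE; open to argument if the CEC rules the death HF-related |
| 3. No intervention-related event needing medical care | Met unless the CEC rules the death intervention-related |
| Safety: not terminated for a safety issue | Met |
| Safety: no treatment-related adverse event | Met unless the CEC attributes the death to the intervention |

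If the CEC rules the death neither HF-related nor intervention-related, the episode is effective = 1 and safe = 1. If it rules the death intervention-related, safety fails. Criterion 3 then turns on whether an unattended death required medical care, which the text does not settle.

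**Step 2. Death before the recovery reading.** Criterion 1 cannot be shown to be met, so the text does not score this episode effective. Its status is undefined, and it may drop out as missing.

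**Step 3. Reproduce the plan's figures.** Table 18: 43 + 62 + 63 + 40 + 25 = 233 crossings, and 233 × 0.45 = 104.9, about 105 episodes. Table 19, first row: the exact Clopper-Pearson 95% interval for 49/70 is 0.579 to 0.804, width 0.225, as stated. All 12 rows reproduce to three decimals. No stated number is wrong; the gap is in the definition.

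**Step 4. Days at risk.** Only deaths after the recovery reading can be miscoded. With PRN on Days 1–3, the window runs to Day 3 + 14 = Day 17. Day 4 to Day 17 is 14 days.

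**Step 5. Expected number.** The documents give no mortality rate. Assume 5–15% per year, spread evenly:

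- expected deaths = episodes × (days / 365) × annual rate
- at 5%: 105 × 14/365 × 0.05 = 0.20
- at 15%: 105 × 14/365 × 0.15 = 0.60

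These are upper limits at the assumed rates. They count deaths from all causes in all 105 episodes, whereas miscoding needs a recovered episode, no IV therapy, no admission, and no CEC link to HF or to the intervention.

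**Step 6. Effect on the rate.** Each miscoded episode is worth 1/N: 1/105 = 0.95 points, 1/100 = 1.0 point, 1/70 = 1.4 points.

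| N | Effective as written | Rate (95% CI) | One death recoded as not effective |
|---|---|---|---|
| 70 | 49 | 0.700 (0.579–0.804) | 0.686 (0.564–0.791) |
| 100 | 90 | 0.900 (0.824–0.951) | 0.890 (0.812–0.944) |
| 105 | 84 | 0.800 (0.711–0.872) | 0.790 (0.700–0.864) |

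The planned interval widths in Table 19 run from 12.7 to 22.5 points.

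**The case against.** **The CEC already has a route.** The event that led to a death goes on an adverse event form. Under Table 15 the CEC adjudicates adverse events for HF and PRN relatedness, so a death from decompensation carries an HF ruling. The opening words of criterion 2 could then catch it. This stands in part: it makes HF deaths ambiguous rather than clearly missed, since the NOTE omits death. It does nothing for a death that is neither HF-related nor intervention-related, or that cannot be classified.

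**Deaths are not hidden.** SAP 7.10 summarises seriousness and relatedness and lists individual adverse events, and SAP 7.1.1 reports disposition. This stands, but a listing does not correct the primary rate.

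**The effect is small and nothing is tested.** This stands. There is no hypothesis and no performance requirement, so no threshold can be crossed.

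**Counting all-cause death makes an HF-focused endpoint a composite.** This is a fair point about the choice of remedy. A sensitivity analysis limited to cardiac or HF-related deaths answers it.

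A reader might also infer more than the documents support:

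- That a death close to the intervention can never enter either primary rate. A death that the CEC attributes to the intervention fails the safety endpoint.
- That the protocol expects such deaths. Section 10.5.2 only defines classes of death and gives no rate.
- That a High risk status implies raised mortality in the window. As described, the risk status concerns HF hospitalisation in the next 30 days, not death.

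**Conclusion.** The gap is real and lies in the wording of a primary endpoint. Following the rule as written, a death after recovery and within the window is coded as effective unless the CEC links it to HF (ambiguous) or to the intervention, and as safe unless the CEC attributes it to the intervention.

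The likely size is at most about 0.2–0.6 episodes in 105, about 1 percentage point each. This rests on an assumed annual mortality of 5–15% at an even rate, about 14 days at risk per episode, and the plan's own forecast of 105 episodes. It would be tempting to say that one such case changes what the study tells the pivotal trial. The planned interval widths and the absence of any decision threshold do not support that. The reason to act is validity: death should not be able to count as success, and the correction is cheap.

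**What to change.** In protocol 13.3.2 and SAP 7.9.1.3:

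- Add to criterion 2 that the subject has not died, from any cause, during the intervention or within 14 days after its completion. State that a death before the recovery reading also makes the episode not effective.
- Use all-cause death in the main analysis. Add a sensitivity analysis that counts only deaths the CEC adjudicates as cardiac or HF-related.
- Beside the two primary rates, list every death in the window with its CEC cause and PRN-relatedness.

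The cost is a sentence or two in each document, one sensitivity analysis and one listing. No new data are needed, because all deaths are already collected and adjudicated. The downside is that an occasional death unrelated to HF counts as not effective; the sensitivity analysis shows how much that matters.

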13.3.3 Performance Requirements

There are no performance requirements for this objective.

13.3.4 Rationale for Performance Criteria

Rational for performance criteria is not applicable for this objective.

13.3.5 Analysis Methods

For each episode that requires intervention as determined by this protocol, the effectiveness of Integrated Diagnostic Medication Intervention Strategy will be evaluated as a binary outcome variable, where 1 = effective and 0 = not effective. During the course of the study, a subject could experience more than one intervention. Therefore, a generalized linear model with the generalized estimating equation (GEE) method will be used to analyze this correlated binary data. The effectiveness rate and its 95% confidence interval (CI) will be calculated based on the log of odds estimated using the GEE.

13.3.6 Determination of Patients/Data for Analysis

All subjects who have received the Integrated Diagnostic Medication Intervention per protocol.

13.3.7 Sample Size

As the above-mentioned, based on the experience from previous studies we expect to observe about 233 OptiVol crossings from 110 enrolled subjects in this trial and of them 105 OptiVol crossings would require Integrated Diagnostic Medication Intervention. There are no data to help us predict the percentage of OptiVol crossings receiving Integrated Diagnostic Medication Intervention or the effectiveness rate of Integrated Diagnostic Medication Intervention Strategy. We consider different scenarios in Table 19 and Figure 9 to estimate the precision on measuring the effectiveness rate of Integrated Diagnostic Medication Intervention Strategy.

The width of 95% CI for the effectiveness rate represents the measurement precision. Using the first row in Table 19 as an example, a total of 70 independent episodes with Integrated Diagnostic Medication Intervention produces a two-sided 95% CI with an actual width of 0.225 when the observed proportion of having effective treatment among those episodes is 0.7. This is based on the exact Clopper-Pearson confidence interval for one proportion assuming independent effectiveness status of Integrated Diagnostic Medication Intervention. Note that each episode is an OptiVol crossing that lead to the initiation of an Integrated Diagnostic Medication Intervention. Note also that for each scenario, we expect a narrower width (i.e. better precision) of 95% CI for the effectiveness rate in the framework of generalized linear model with GEE method. This is because GEE method takes the correlation among the effectiveness status of multiple episodes from the same subject into account, thus presumably results in a smaller standard error of the effectiveness rate.

Figure 9 is a visual illustration of Table 19.

Table 19: Table of the 95% Confidence Interval for 70-100 independent episodes

Confidence Level	Size (N)	Actual Width	Sample Proportion (P)	Lower Limit	Upper Limit
0.950	70	0.225	0.700	0.579	0.804
0.950	70	0.199	0.800	0.687	0.886
0.950	70	0.154	0.900	0.805	0.959
0.950	80	0.210	0.700	0.587	0.797
0.950	80	0.186	0.800	0.696	0.881
0.950	80	0.143	0.900	0.812	0.956
0.950	90	0.198	0.700	0.594	0.792
0.950	90	0.174	0.800	0.702	0.877
0.950	90	0.135	0.900	0.819	0.953
0.950	100	0.187	0.700	0.600	0.788
0.950	100	0.165	0.800	0.708	0.873
0.950	100	0.127	0.900	0.824	0.951

[figure not shown]

Figure 9: Graph of the 95% Confidence Interval for 70 to 100 independent episodes

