13.4.7 Sample Size

The same estimates on the precision of measuring effectiveness rate of Integrated Diagnostic Medication Intervention Strategy under different scenarios illustrated in Table 19 and Figure 9 above are applicable to the safety rate as well. Again, using the first row in Table 19 as an example, a total of 70 independent episodes with Integrated Diagnostic Medication Intervention produces a two-sided 95% CI with an actual width of 0.225 when the observed proportion of having safe treatment among those episodes is 0.7.

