7.9.1.4. Analysis Methods

For each episode that requires intervention as determined by this protocol, the effectiveness of Integrated Diagnostic Medication Intervention Strategy will be evaluated as a binary outcome variable, where 1 = effective and 0 = not effective. During the course of the study, a subject could experience more than one intervention. Therefore, a generalized linear model with the generalized estimating equation (GEE) method will be used to analyze this correlated binary data. The effectiveness rate and its 95% confidence interval (CI) will be calculated based on the log of odds estimated using the GEE.

In the main analysis, there will be no covariates in the generalized linear model, only intercept (β_0) will be estimated. Let π = probability (Integrated Diagnostic Medication Intervention Strategy is effective), then:

$$\beta_0 = \log\left(\frac{\pi}{1 - \pi}\right)$$

To solve for π :

$$\pi = \frac{e^{\beta_0}}{1 + e^{\beta_0}}$$

The analysis will be conducted using PROC GENMOD procedure in SAS similar to the following:

```

proc genmod data=effectiveness descending;
  class pt;
  model effective = /dist=bin link=logit type3;
  repeated subject=pt /type=exch modelse;
  output out=predict predicted=pr_success lower=lower_CI upper=upper_CI;
run;

```

In this procedure, 'effective' is the outcome variable with 1=effective and 0=not effective. 'dist=bin' and 'link=logit' indicates this generalized linear model is based on a logistic regression for binomial distribution. In the 'repeated' statement, 'subject=pt' assumes observations from the same subject are correlated, and 'type=exch' means parameter coefficient(s) in the model will be estimated using GEE. 'predicted=' in the 'output' statement gives the estimated probability of Integrated Diagnostic Medication Intervention Strategy being effective, and its 95% confidence interval based on the parameter estimate of the intercept are from 'lower=' and 'upper='.

If it turns out that the majority of subjects included in the analysis received a single Integrated Diagnostic Medication Intervention, a sensitivity analysis will be conducted through the common logistic regression assuming independent interventions within the same subject. In addition, secondary analysis may be considered to explore the association of covariates such as NYHA class with the effectiveness endpoint.

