7.9.1.6. Sample Size and Measurement Precision

[figure not shown]
There are no data to help us predict the percentage of OptiVol crossings receiving Integrated Diagnostic Medication Intervention or the effectiveness rate of Integrated Diagnostic Medication Intervention Strategy. Different scenarios have been considered in Table 2 and Figure 2 to estimate the precision on measuring the effectiveness rate of Integrated Diagnostic Medication Intervention Strategy. Figure 2 is a visual illustration of Table 2.

The width of 95% CI for the effectiveness rate represents the measurement precision. Using the first row in Table 2**Error! Reference source not found.** as an example, a total of 70 independent episodes with Integrated Diagnostic Medication Intervention produces a two-sided 95% CI with an actual width of 0.225 when the observed proportion of having effective treatment among those episodes is 0.7. This is based on the exact Clopper-Pearson confidence interval for one proportion assuming independent effectiveness status of Integrated Diagnostic Medication Intervention. Note that each episode is an OptiVol crossing that lead to the initiation of an Integrated Diagnostic Medication Intervention. Note also that for each scenario, we expect a narrower width (i.e. better precision) of 95% CI for the effectiveness rate in the framework of generalized linear model with GEE method. This is because GEE method takes the correlation among the effectiveness status of multiple episodes from the same subject into account, thus presumably results in a smaller standard error of the effectiveness rate.

Table 2: Measurement Precision of Effectiveness Rate for 70-100 Independent Episodes

Sample

Confidence Level	Size (N)	Actual Width (P)	Proportion	Lower Limit	Upper Limit
0.950	70	0.225	0.700	0.579	0.804
0.950	70	0.199	0.800	0.687	0.886
0.950	70	0.154	0.900	0.805	0.959
0.950	80	0.210	0.700	0.587	0.797
0.950	80	0.186	0.800	0.696	0.881
0.950	80	0.143	0.900	0.812	0.956
0.950	90	0.198	0.700	0.594	0.792
0.950	90	0.174	0.800	0.702	0.877
0.950	90	0.135	0.900	0.819	0.953
0.950	100	0.187	0.700	0.600	0.788
0.950	100	0.165	0.800	0.708	0.873
0.950	100	0.127	0.900	0.824	0.951

Figure 2: Illustration of Table 2

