7.9.2.4. Analysis Methods

Similar to the effectiveness endpoint of Integrated Diagnostic Medication Intervention Strategy, the safety endpoint of Integrated Diagnostic Medication Intervention Strategy is a correlated binary outcome with 1=safe and 0=not safe. It will be analyzed using a generalized linear model with GEE method. The safety rate and its 95% CI will be calculated based on the log of odds estimated using GEE.

Similar to Section 7.9.1.4, the analysis will be conducted using PROC GENMOD:

```
proc genmod data=safety descending;
  class pt;
  model safe = /dist=bin link=logit type3;
  repeated subject=pt /type=exch modelse;
  output out=predict predicted=pr_success lower=lower_CI upper=upper_CI;
run;
```

where 'safe' is the outcome variable with 1=safe and 0=not safe.

Again, if it turns out that the majority of subjects included in the analysis received a single Integrated Diagnostic Medication Intervention, a sensitivity analysis will be conducted through the common logistic regression assuming independent interventions within the same subject. In addition, secondary analysis may be considered to explore the association of covariates such as NYHA class with the safety endpoint.

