7.9.2.6. Sample Size and Measurement Precision

The estimated precision of measuring effectiveness rate of Integrated Diagnostic Medication Intervention Strategy under different scenarios illustrated in Table 2 and Figure 2 are applicable to the safety rate as well. Using the first row in Table 2 as an example, a total of 70 independent episodes with Integrated Diagnostic Medication Intervention produces a two-sided 95% CI with an actual width of 0.225 when the observed proportion of having safe treatment among those episodes is 0.7.

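### The plan expects within-subject correlation to narrow the 95% CI for the effectiveness rate; for the planned intercept-only GEE, positive correlation widens it

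*Protocol*

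**What the plan says.** Protocol Table 19, repeated as SAP Table 2, gives 95% CI widths for the effectiveness rate from the "exact Clopper-Pearson confidence interval for one proportion assuming independent effectiveness status". In its first row, 70 episodes with an observed rate of 0.7, the interval "produces a two-sided 95% CI with an actual width of 0.225". Both documents add that "for each scenario, we expect a narrower width (i.e. better precision) of 95% CI for the effectiveness rate" under GEE. The reason given in both is that GEE allows for correlation among episodes from the same subject and "thus presumably results in a smaller standard error of the effectiveness rate".

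SAP 7.9.1.4 fixes the model: "there will be no covariates in the generalized linear model, only intercept" is estimated, with a logit link, clustering by subject and an exchangeable working correlation. If most treated subjects have a single intervention, "a sensitivity analysis will be conducted through the common logistic regression assuming independent interventions within the same subject" (SAP 7.9.2.4 for safety; SAP 7.9.1.4 plans the same for effectiveness).

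Protocol 13.4.7 and SAP 7.9.2.6 say that the tabulated precision figures "are applicable to the safety rate as well". They do not repeat the expectation of a narrower interval.

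**The concern.** Allowing for correlation can reduce the standard error of a within-subject contrast. This model contains no contrast, only one rate. Repeated episodes from a subject who tends to respond, or tends not to, add less information than the same number of episodes from different subjects. Positive correlation therefore lowers the effective number of episodes and widens the interval.

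The study has no hypothesis and no power calculation, so these widths are its only quantitative statement of precision, and they serve both primary objectives. A reader is led to treat them as cautious. The same reasoning could lead a reader to take the independence-based logistic regression as a conservative cross-check when, under positive correlation, its interval is too short.

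**Working it through.** **Inputs**

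- Protocol Table 18: 43, 31, 21, 10 and 5 subjects with 1, 2, 3, 4 and more than 4 crossings (the last taken as 5, as in the table). Total: 110 subjects, 233 crossings.
- Protocol 13.1: 45% of crossings lead to intervention, so 233 × 0.45 = 104.85, the plan's 105.
- Within-subject ICC (ρ): not in the documents. Assumed values are 0.1, 0.3 and 0.5.

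**Plan's own figures.** Clopper-Pearson limits for 49 of 70 are 0.579 and 0.804, width 0.225. All 12 rows of Table 19 reproduce.

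**Episodes per treated subject.** Two cases bracket the range.

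- *Thinned:* each crossing independently has a 45% chance of leading to intervention. This gives 47.3, 18.7, 5.3, 1.0 and 0.1 subjects with 1 to 5 episodes: 72.3 subjects and 104.85 episodes. The share with one episode is 47.3/72.3 = 65%.
- *Concentrated:* the unthinned Table 18 sizes, scaled to N, as if the HF-related crossings fell in the same subjects. This is an upper bound that nothing in the documents supports.

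**Design effect** for an intercept-only exchangeable GEE, with m the episodes per subject and sums over subjects:

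DE = Σm / Σ[m/(1 + (m − 1)ρ)]

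Thinned, ρ = 0.3: the denominator is 47.30 + 28.70 + 9.93 + 2.05 + 0.21 = 88.18, so DE = 104.85/88.18 = 1.19.

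**Width on the planned scale.** With b = logit(P) and SE = √[DE/(N·P(1 − P))], the width is expit(b + 1.96 SE) − expit(b − 1.96 SE). At N = 70, P = 0.7, b = 0.847 and N·P(1 − P) = 14.7:

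- ρ = 0: SE = √(1/14.7) = 0.261, limits 0.583 and 0.796, width 0.212.
- ρ = 0.3, thinned: SE = √(1.189/14.7) = 0.284, limits 0.572 and 0.803, width 0.231.

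| ICC | DE thinned | DE concentrated | Width, N=70, P=0.7 (printed 0.225) | Width, N=100, P=0.9 (printed 0.127) |
|---|---|---|---|---|
| 0 | 1.00 | 1.00 | 0.212 | 0.121 |
| 0.1 | 1.07 | 1.16 | 0.220 to 0.228 | 0.126 to 0.131 |
| 0.3 | 1.19 | 1.43 | 0.231 to 0.253 | 0.133 to 0.147 |
| 0.5 | 1.28 | 1.66 | 0.240 to 0.272 | 0.138 to 0.159 |

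In each range the lower figure is the thinned case and the higher the concentrated case. The width rises with ρ throughout; only negative ρ reduces the SE (multiplier 0.955 at ρ = −0.1, thinned). In the thinned case 100 episodes act like 100/1.189 = 84 at ICC 0.3 and 100/1.281 = 78 at 0.5.

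**Crossover.** Over the 12 rows the formula width passes the printed width at an ICC of 0.13 to 0.19 (thinned) or 0.06 to 0.08 (concentrated). Below that, the GEE interval is shorter only because a logit-scale interval is shorter than the conservative exact one; the gap is already there at ρ = 0 (0.212 against 0.225).

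**Simulation** (4000 beta-binomial data sets per setting, exchangeable GEE with robust SE, N = 70, P = 0.7). Mean GEE widths at ICC 0, 0.1, 0.3 and 0.5 were 0.205, 0.213, 0.225 and 0.234 (thinned) and 0.204, 0.220, 0.245 and 0.263 (concentrated). The independence-based width stayed at 0.21 throughout. In the thinned case its coverage fell to 92.7% at ICC 0.3 and 90.5% at 0.5, against 94 to 95% for the GEE. The thinned simulated widths lie 0.006 to 0.007 below the formula at every ICC, including zero, so that offset is not a correlation effect. It is what one would expect of a robust SE from about 48 subjects (70 episodes at 1.45 each).

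**The case against.** The strongest reply is that the prediction, read literally, often comes true. In the thinned case the GEE interval is narrower than the table up to an ICC of 0.13 to 0.19 by formula. By simulation at N = 70, P = 0.7 it only reaches the printed 0.225 at about 0.3, and even at 0.5 it exceeds it by about 0.01. The ICCs are assumed. A high one cannot be presumed, because the plan allows a subject's prescription to change between episodes. The wording is also hedged as an expectation. All of this stands, and it limits the size of the problem. It does not rescue the reason given, since the shorter interval at low ICC owes nothing to correlation, and it does not support an expectation for every scenario.

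It is also fair to say that the SAP never calls the independence-based regression cautious, and that its trigger, mostly single interventions, is where ignoring correlation costs least. That analysis is therefore not an error in itself; a note on how to read it is enough. The safety sections likewise only reuse a correct table labelled as independent.

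Finally, little depends on the sentence. There is no hypothesis, power target or numerical stopping threshold, and the reported CI will come from the GEE.

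**Conclusion.** The concern holds. Protocol 13.3.7 and SAP 7.9.1.6 give the direction of the correlation effect the wrong way round for the planned model, and nothing elsewhere corrects it. That conclusion needs only a positive ICC and some subjects with more than one episode.

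The size does depend on assumptions: the ICC, independent thinning at 45%, and more than four crossings counted as five. On the thinned case, the better supported of the two, the SE is larger than under independence by about 4%, 9% and 13% at ICC 0.1, 0.3 and 0.5 (√1.07, √1.19, √1.28). The concentrated figures are an upper bound and deserve little weight. With about 65% of treated subjects expected to have one intervention, the independence-based sensitivity analysis is likely to be run, so its reading matters. The GEE analysis remains valid and the printed tables are correct.

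**What to change.** In Protocol 13.3.7 and SAP 7.9.1.6, delete the two sentences that expect a narrower width and a smaller standard error. State instead that positive within-subject correlation widens the CI of a single rate.

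Keep Table 19 and SAP Table 2 as the independence reference. Add columns with the expected logit-GEE widths at ICC 0.1, 0.3 and 0.5, using the design effect above with cluster sizes from Table 18, and label the ICCs and the thinning as assumptions. Say in Protocol 13.4.7 and SAP 7.9.2.6 that the added columns also apply to the safety rate.

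In SAP 7.9.1.4 and 7.9.2.4, note that the ordinary logistic regression is the optimistic analysis under positive correlation.

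The cost is two sentences in each document, the added columns and a short note. Stated precision becomes slightly less favourable at moderate correlation. No extra subjects are needed and the planned analysis does not change.
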